1 INTRODUCTION

1.1 Study Purpose

Medtronic, Inc. is sponsoring a quality improvement study called the “Registry to Improve the Adoption of Consensus Treatment Guidelines” (IMPROVE Brady). It is hypothesized that the use of a practice-specific process improvement intervention consisting of education, diagnostic algorithm(s) and documentation tools that advocate and reinforce adherence to consensus treatment guidelines will improve the quality of care for patients with sinus node dysfunction (SND).

The study is expected to provide evidence to support claim(s) that:

- Education and process improvement initiatives can improve the diagnosis of and appropriate therapy application for SND
- The quality improvement methods studied have general applicability and can be used by all centers
- Appropriate treatment minimizes caregiver burden
- Appropriate treatment improves quality of life (QOL) and functional status compared to pre-implant

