During Phase II a patient survey assessing the subject's quality of life and functional status, will be completed by subjects meeting an SND indication for pacing therapy and being implanted with a market released pacemaker from the Medtronic family of devices. The patient survey must be completed before the implant procedure and again at 6 months post-implant.

The caregiver of the subject being implanted with the market released pacemaker from the Medtronic family of devices will be asked to participate in a caregiver survey. The purpose of the survey is to assess how providing care to the person receiving the pacemaker impacts the caregiver. Prior to completing the survey an Informed Consent or Patient Data Release will need to be signed by the caregiver. The caregiver survey will be completed prior to the implant procedure and again at 6 months post-implant. The same caregiver must complete the pre and post implant surveys of the same patient.

For subjects enrolled during Phase II collection of diagnostic assessment data will be complete 6 months after last enrollment for the geography/country. At that time, any subjects without a diagnosis will be exited from the study. Collection of implant data will be complete 6 months after the last Phase II diagnosis for the respective geography/country. Any subjects not implanted by the end of the 6 months will be exited from the study. The Geography/country study timeline (Figure 2) depicts the geography/country timeline.

Figure 2: Geography/country study timeline

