5.7 Study Exit

Subjects may be exited from the study for any of the following situations, including but not limited to:

- Subject does not meet an indication for pacing therapy
- Subject meets an indication for pacing but not a SND indication for pacing therapy
- Subject has met a SND indication for pacing therapy and did not receive a market released pacemaker from the Medtronic family of devices
- Subject has met a SND indication for pacing therapy but will not be receiving pacing therapy
- Subject has completed the final scheduled follow-up visit.

- Geography/country completion of Phase I follow-up
- Study Closure
- Subject lost to follow-up
- Subject death
- Subject did not meet inclusion/exclusion criteria
- Subject chooses to withdraw (e.g., consent withdrawal, relocation to another geographic location)
- Investigator deems withdrawal necessary (e.g., medically justified, failure of subject to maintain adequate study compliance)

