8.5.6.1. Analysis Methods

A. Statistical Methodology

Descriptive statistics will be used to summarize the difference in caregiver burden between pre-implant and 6 months post-implant. The Zarit Burden Interview is a 22 question survey, with each question scored on a scale of 0 to 4. The total score is the sum of all 22 question responses. A t-statistic will test the difference between the total score of the survey between pre-implant (zarit0) and 6 month post-implant (zarit6). [REDACTED]

[REDACTED]

The primary analysis will deal with missing values by scaling the total score of the non-missing responses. If at least 50% of the survey has been completed, the total score of the non-missing responses will be multiplied by (22/number of non-missing responses). If less than half of the questions were answered, the survey will not be included in the analysis. Missing values will be dealt with using a multiple imputation procedure as a sensitivity analysis.

B. Determination of Patients/Data for Analysis

Subjects in Phase II who opt to receive an indicated therapy and are implanted with a market released pacemaker from the Medtronic family of devices will be followed from implant to 6 months post-implant. The primary caregiver of these subjects will be asked to complete a questionnaire that assesses caregiver burden at the time of implant and 6 months post-implant.

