8.5.7.1. Analysis Methods

A. Statistical Methodology

Descriptive statistics will be used to summarize the difference in QOL and functional status between pre-implant and 6 months post-implant. The SF-12 survey results will be compared at implant and at six

This document is electronically controlled. Printed copies are considered uncontrolled.

Confidential

months of follow-up. A t-statistic will test the difference in the survey scores between the two time points. The eight sub-domains of the SF-12 may also be tested.

Composite scores are calculated by first appropriately summarizing eight scales from the individual SF-12 questions.

- Physical Functioning (PF) - Items 2a+2b
- Role Physical (RF) - Items 3a+3b
- Bodily Pain (BP) - Item 5
- General Health (GH) - Item 1
- Vitality (VT) - Item 6b
- Social Functioning (SF) - Item 7
- Role Emotional (RE) - Items 4a+4b
- Mental Health (MH) - Items 6a+6b

If at least half of the items within any scale have been completed, any missing values within those scales can be imputed as the average response of all remaining questions from that scale for that respondent within the survey taken on that visit (Chapter 6 of SF-36 Health Survey Manual and Interpretation Guide).

Once the eight scales have been summarized, they are each normalized by their 1998 general US population means and standard deviations, and a linear combination of the scales are combined to calculate the composite physical and mental scores (Chapter 8 of How to Score Version 2 of the SF-12 Health Survey).

B. Determination of Patients/Data for Analysis

Subjects in Phase II who opt to receive an indicated therapy and are implanted with a market released pacemaker from the Medtronic Family of devices will be followed from implant to 6 months post-implant. These subjects will be asked to complete a questionnaire that assesses their QOL at the time of implant and 6 months post-implant.

This document is electronically controlled. Printed copies are considered uncontrolled.

Confidential

[REDACTED]

This document is electronically controlled. Printed copies are considered uncontrolled.

Confidential

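### The planned claims that treatment minimizes caregiver burden and improves quality of life rest on an uncontrolled before/after change in implanted Phase II subjects, which cannot be attributed to treatment

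*Protocol*

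**What the plan says.** Protocol 1.1 introduces its list with "The study is expected to provide evidence to support claim(s) that". Two of the four entries concern the effect of treatment: "Appropriate treatment minimizes caregiver burden" and "Appropriate treatment improves quality of life (QOL) and functional status compared to pre-implant".

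Protocol 4.3 sets out who is surveyed: "During Phase II a patient survey assessing the subject's quality of life and functional status, will be completed by subjects meeting an SND indication" and being implanted with a sponsor pacemaker. On timing it says "The patient survey must be completed before the implant procedure and again at 6 months post-implant". The caregiver survey follows the same two time points. Protocol 5.5 and 5.6 mark the surveys and the 6-month visit as Phase II only. Protocol 5.7 allows exit when "Subject has met a SND indication for pacing therapy but will not be receiving pacing therapy", and also when the subject did not receive a sponsor device.

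The documents differ on whether these objectives are tested:

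- Protocol 4.1 places all the secondary objectives under a heading that says hypotheses have been specified in advance for testing.
- Protocol 11.2 plans only descriptive statistics for Secondary Objectives 4 and 5.
- SAP 8.5.6.1 keeps the descriptive statistics and adds, for the Zarit score, "A t-statistic will test the difference between the total score of the survey between pre-implant (zarit0) and 6 month post-implant (zarit6").
- SAP 8.5.7.1 does the same for the SF-12: "A t-statistic will test the difference in the survey scores between the two time points". It also allows tests of the eight sub-domains.

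**The concern.** Both claims are causal. The quality-of-life claim names its reference (the pre-implant value), but saying that treatment improves the score still credits the change to treatment. The caregiver claim has no such qualifier, and minimizing burden goes beyond any pre/post difference.

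A one-group t-test asks whether the mean change differs from zero. It cannot say why. No survey score exists for an unpaced subject, for a Phase I subject, or for the caregiver of either. If the tests come out significant, nothing in the readable text limits how the result may be read, and the list in Protocol 1.1 invites a treatment-benefit reading. Protocol 2 itself names the randomized trial as the standard for causal conclusions and notes that conclusive randomized evidence for pacing in this condition is lacking.

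**Working it through.** **Step 1. Is there a comparator anywhere?**

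- Data collection (Protocol 5.2, Table 1, read with 5.5 and 5.6): patient and caregiver surveys at implant and at the scheduled follow-up, for implanted subjects in Phase II. There is no other survey point.
- Bias control (Protocol 4.4): centers serve as their own control. That works for diagnosis and implant rates, which both phases record, but not for surveys, which Phase I lacks.
- Temporal confounding (SAP 8.2.1): the interrupted time-series model covers the diagnosis and implant rates only.
- Drug changes: Protocol 5.10 restricts only investigational drugs. Table 1 records cardiovascular drugs at enrollment, diagnostic assessment and implant, but not at the 6-month visit where the outcome is measured.
- Redactions: parts of SAP 8.5.6.1 and 8.5.7.1 are blacked out. They could hold further analyses, but the visible data collection provides no untreated scores to analyse.

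**Step 2. How many pairs?** The documents give no sample size, SD, effect size or power for the surveys, so there is no planned figure to reproduce. SAP 8.5.2.2 gives 200 Phase II subjects with the diagnosis and 26% implanted: 200 × 0.26 = 52. With the 10% attrition of SAP 8.2.1, 52 × 0.9 = 46.8, or about 47 pairs. At the 10% uptake assumed for Phase I it would be 200 × 0.10 = 20. These are figures per geography; under SAP section 6 only South Asia entered Phase II.

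**Step 3. Smallest change that is significant.** I assume a paired test at two-sided 0.05, since neither is stated for the surveys. The threshold in SDs of the change score is t(0.975, n−1)/√n:

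- n = 47: 2.013/√47 = 0.29
- n = 52: 2.008/√52 = 0.28
- n = 20: 2.093/√20 = 0.47

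**Step 4. Illustration with zero device effect.** Suppose the group's baseline lies k SD worse than the reference mean towards which scores regress, with test-retest correlation r.

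- Expected change = k(1−r) SD
- SD of change = √(2(1−r)) SD
- Standardized change d = k(1−r)/√(2(1−r))
- Probability of a significant favourable result = upper tail of the noncentral t with n−1 degrees of freedom and noncentrality d√n

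Worked case, k = 1, r = 0.6, n = 52: change 0.40 SD; d = 0.40/√0.80 = 0.447; noncentrality 0.447 × √52 = 3.22; probability 0.89.

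| k | n | r = 0.6 | r = 0.7 | r = 0.8 |
|---|---|---|---|---|
| 0.25 | 47 | 0.11 | 0.10 | 0.08 |
| 0.25 | 52 | 0.12 | 0.10 | 0.08 |
| 0.5 | 47 | 0.32 | 0.25 | 0.18 |
| 0.5 | 52 | 0.35 | 0.28 | 0.20 |
| 1 | 47 | 0.85 | 0.74 | 0.56 |
| 1 | 52 | 0.89 | 0.78 | 0.61 |

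The nominal rate in the favourable direction is 0.025. With 20 pairs and k = 1 the row is 0.48, 0.38, 0.27. The values of k and r are assumptions; the documents give neither.

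**The case against.** The best defence is that the text is modest. Protocol 1.1 speaks of evidence to support claims, not proof. The quality-of-life claim says what it is compared with, and that is what is measured. The SAP states the objectives neutrally, as evaluating change, and retains the descriptive summaries. Protocol 2 presents the study as effectiveness research. All this is true, but it does not remove the causal wording of the two claims, and the caregiver claim has no reference at all.

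The defence does rule out several stronger readings that a reader might infer:

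- **Natural recovery will produce the benefit.** Protocol 2 calls the symptoms chronic and non-specific, so recovery is not the documented course. Regression to the mean, fluctuation, expectation after an unblinded implant, other treatment changes and completer selection are the apt list, and no passage shows that all of them favour improvement.
- **The first survey is taken at a low point.** The 30-day symptom criterion in Protocol 4.2 applies at enrollment. The survey comes at implant, after a diagnostic process with no fixed timing. A low baseline is possible but not shown.
- **A false positive is likely.** Only the k = 1 rows exceed one half, and 0.89 is the extreme cell. At k = 0.25 the figure is 0.08 to 0.12.
- **The illustration covers caregivers.** Caregivers are not selected on burden, so it is not shown to apply to Zarit scores.
- **Unpaced subjects are always exited.** Protocol 5.7 says they may be.

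The defence is also right that a 95% confidence interval in place of the t-test changes no decision, since the interval excludes zero exactly when the paired test rejects. Nor would change plotted by baseline score separate drift from benefit, because measurement error alone produces a slope.

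**Conclusion.** The point holds as one about attribution. The surveys can describe how scores changed in implanted Phase II subjects; they cannot support the statement that treatment caused the change, however large or significant it is. That conclusion needs no numerical assumption, because it follows from the absence of any untreated scores.

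The size of the risk is uncertain. On the assumed grid the chance of a significant favourable change with no device effect is about 0.08 to 0.89, roughly 3 to 35 times the nominal 0.025 (0.08/0.025 = 3.2; 0.89/0.025 = 35.6). It rests on assumed baseline displacement, correlation, pairing and alpha, and on planning counts for implants, and it speaks to patient scores only. The documents do not support saying that a spurious result is probable. Two of the four claims in Protocol 1.1 are affected, both on secondary objectives; the primary objectives are not.

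**What to change.** 1. In Protocol 1.1, replace the two claims with: *Describe the change in caregiver burden, QOL and functional status from pre-implant to 6 months in implanted Phase II subjects; this uncontrolled change will not be attributed to treatment.* The second clause does the real work.
2. In Protocol 4.1, move Secondary Objectives 4 and 5 out of the heading that announces hypothesis tests, so that it agrees with Protocol 11.2.
3. In SAP 8.5.6.1 and 8.5.7.1, label the paired change as descriptive. Report the mean with a 95% confidence interval and the number of implanted subjects lacking a 6-month survey.

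The cost is wording in two documents, with no new data. The sponsor gives up a treatment-benefit claim on secondary objectives that this design cannot carry.

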1.2 Study Scope

The study may be conducted in countries located in Central and Eastern Europe (CEE), Greater China, India, Latin America, Asia, and Middle East and Africa (MEA). Countries from other geographies may be added in the future. The distribution of centers will be approximately 10 per geography or country and is determined by local evidence needs.

Approximately 1,650 subjects per geography/country, or up to 14,850 subjects worldwide, will be enrolled in the study. An enrollment target of 6 subjects per center per month is desired to make center-specific outcomes more meaningful and reliable in measuring changes in diagnostic rates and patient acceptance of indicated therapy. Centers that enroll faster than others will be allowed to enroll until 20% of the sample size for the geography/country has been reached for a maximum of 330 subjects per site.

All study subjects will be followed until the study exit criteria are met or until official study closure. Study closure is defined as closure of a clinical study that occurs when Medtronic and/or regulatory requirements have been satisfied per the Clinical Investigation Plan and/or by a decision by Medtronic or regulatory authority, whichever occurs first. The expected study duration per geography/country, from first enrollment to last follow-up, is approximately 4.5 years per geography/country.

2 BACKGROUND AND JUSTIFICATION

The World Health Survey of Cardiac Pacing and Cardioverter-Defibrillators suggests that adoption of pacing therapy in emerging countries is lower than that

of developed countries. New device implants per million in emerging countries are 17, 31, 159 and 287 for India, China, Russia and Argentina respectively compared to 702, 782, 744 and 627 for the respective developed countries of Sweden, France, Italy and Belgium. The population for these countries in millions is as follows: 1,200 in India, 1,300 in China, 142 in Russia, and 40 in Argentina, 9 in Sweden, 62 in France, 60 in Italy and 10 in Belgium¹. The size of the population in the emerging countries combined with data from the World Health Survey, suggests that there is an opportunity to improve adoption to consensus treatment guidelines in the emerging countries. Adoption of the pacing indications for Sinus Node Dysfunction (SND) may not be optimal due to the chronic non-specific nature of the symptoms and the lack of conclusive randomized trials supporting the efficacy of pacemaker therapy in SND patients^{2,3,4}. Within the developed geographies, 21-40% of subjects participating in clinical studies receiving pacing therapy had met the indication for sinus node dysfunction. The wide range may demonstrate that SND can be a difficult indication to identify^{1, 5, 6, 7, 8, 9}.

A recent process improvement clinical study, IMPROVE HF, demonstrated that implementation of a defined and scalable practice-specific quality improvement process in the outpatient heart failure cardiology setting significantly improved the use of evidence-based therapies in eligible patients with systolic heart failure¹⁰. A baseline chart review was conducted at 167 sites, involving 34,810 patients. Physicians then attended an educational workshop, where they set treatment goals and developed a customized clinical care pathway for their practice. Sites were also provided with heart failure disease state management tools that were designed to help improve the quality of care administered to their heart failure patients. Participation did not require that any specific procedure or assessment be done¹¹. After the intervention occurred, there was evidence of significant improvements in the adoption of guideline based care. Perhaps a similar clinical trial on SND developed for the emerging countries could improve the adoption of the American College of Cardiology (ACC)/American Heart Association (AHA)/Heart Rhythm Society (HRS) Guidelines for Device Based Therapy of

1 Mond HG and Proclemer A. The 11th World Survey of Cardiac Pacing and Implantable Cardiac Defibrillators: Calendar Year 2009 A World Society of Arrhythmia's Project. *Pacing Clin Electrophysiol* 2001 Aug;34:1013-1027

2 Mangrum JM. The Evaluation and Management of Bradycardia. *New England Journal of Medicine* 2010 May;362(10):703-709

3 Epstein et al. ACC/AHA/HRS 2008 Guidelines for Device-Based Therapy of Cardiac Rhythm Abnormalities. *Heart Rhythm* 2008;5:e1-e62.

4 Vardas PE. Guidelines for cardiac pacing and cardiac resynchronization therapy. *European Heart Journal* 2007 Sep;28(18):2256-95.

5 Nowak et al. Do gender differences exist in pacemaker implantation?. *Europace* 2010 Feb;12(2):210-5

6 Levander-Lindgren et al. Bradyarrhythmia profile and associated disease in 1265 patients with cardiac pacing. *Pacing Clin Electrophysiol* 1988 Dec;11(12):2207-15

7 Sutton et al. Electrophysiological and haemodynamic basis for application of new pacemaker technology in sick sinus syndrome and AV block. *Br Heart J* 1979 May;41(5):600-12

8 Coma et al. Spanish Pacemaker Registry. Fifth Official Report of the Spanish Society of Cardiology Working Group on Cardiac Pacing. *Rev Esp Cardiol* 2008 Dec;61(12):1315-28

3 SYSTEM DESCRIPTION AND INTENDED USE

3.1 Device Description

Subjects meeting an ACC/AHA/HRS or ESC indication for pacing therapy may be implanted with any pacemaker from the Medtronic family of devices that are market released and any market released lead. There are no programming requirements for this study. All devices are used according to medical, technical and ethical standards without any change to the approved use of the device.

3.2 Medtronic Programmers

Medtronic programmers will need to be available at each implanting center to support study data collection requirements. Programmers will be used to interrogate, program devices and save device data to a disk or USB. All commercially released Medtronic programmers are available for use in this study.

4 METHODOLOGY

The IMPROVE Brady study is a prospective, interventional, sequential, post market study that may be conducted in CEE, Greater China, India Latin America, Asia and MEA. Additional countries from other geographies may be added in the future. Any market released pacemaker from the Medtronic family of devices may be used in this study. It is hypothesized that the use of a practice-specific process improvement intervention consisting of education, diagnostic algorithm(s) and documentation tools that advocate and reinforce adherence to consensus

¹² Nallamothu, et al. Beyond the Randomized Clinical Trial: The Role of Effectiveness Studies in Evaluating Cardiovascular Therapies. Circ 2008;118;1294-1303.

treatment guidelines will improve the quality of care for patients with sinus node dysfunction (SND).

The study will be conducted in compliance with the Clinical Investigation Plan, Clinical Trial Agreement, approved labeling, latest version of the Declaration of Helsinki, and laws and regulations of the country in which the study is conducted, including data protection laws.

Principles of the Declaration of Helsinki have been incorporated into this study by means of the patient informed consent/Patient Data Release process, IRB/MEC approval (if required), study training, clinical trial registration, risk benefit assessment, and publication policy, etc.

The study may enroll up to 14,850 subjects worldwide. Once enrolled, Phase I subjects may be followed for approximately 1.5 years and Phase II subjects may be followed for approximately 3 years per geography/country. IMPROVE Brady is anticipated to be completed in Spring 2017 across all geographies. Subject data will be collected at enrollment/baseline, diagnostic assessment visits, implant visit and a scheduled follow up visit. Data will continue to be collected until one of the exit criteria has been met (Section 5.7).

IMPROVE Brady requires measurement of Thyroid Stimulating Hormone (TSH & T4) and hemoglobin (HGB) prior to an IPG implant. The bloodwork can be done at any time during the diagnostic process as determined by the sites standard of care. IMPROVE Brady does not mandate specific requirements regarding any other procedures, subject visits to the clinic, clinical treatment of subjects or device programming (if applicable). Clinical data will be collected using electronic case report forms.

Centers will be eligible to enroll subjects in IMPROVE Brady upon Medtronic's receipt of required center activation materials and written approval.

